8.3.5.2 Circulating antibody detection and characterization

Spotted antigen arrays will be used to detect circulating antibodies will be performed on sera derived from the pretreatment and post-cystectomy timepoints. After standard preprocessing of the protein array data, Cluster and Treeview software will be used for unsupervised clustering of the data with Pearson correlation and complete linkage. For each array, an antigen is identified as being detected if its value is above the median. To determine the number of up- and downmodulated antibodies, the difference in log₂ intensity values of pretreatment and post-treatment samples will be taken for each patient to identify antigens that are detected differentially due to treatment. Number of antibodies with at least 2- or 4-fold difference between pretreatment and post-treatment samples will be compared between clinical responders and nonresponders by performing two-sided Wilcoxon rank sum test.

9 Study Management

9.1 Pre-study Documentation

This study will be conducted in accordance with the ethical principles that have their origin in the Declaration of Helsinki as stated in 21 CFR §312.120(c)(4); consistent with GCP and all applicable regulatory requirements.

Before initiating this trial, the Investigator will have written and dated approval from the Institutional Review Board for the protocol, written informed consent form, subject recruitment materials, and any other written information to be provided to subjects before any protocol related procedures are performed on any subjects.

The clinical investigation will not begin until either FDA has determined that the study under the Investigational Drug Application (IND) is allowed to proceed or the Investigator has received a letter from FDA stating that the study is exempt from IND requirements.

The Investigator must comply with the applicable regulations in Title 21 of the Code of Federal Regulations (21 CFR §50, §54, and §312), GCP/ICH guidelines, and all applicable regulatory requirements. The IRB must comply with the regulations in 21 CFR §56 and applicable regulatory requirements.

9.2 Institutional Review Board Approval

The protocol, the proposed informed consent form, and all forms of participant information related to the study (e.g. advertisements used to recruit participants) will be reviewed and approved by the UCSF IRB. Prior to obtaining IRB approval, the protocol must be approved by the Helen Diller Family Comprehensive Cancer Center Site Committee and by the Protocol Review Committee (PRC). The initial protocol and all protocol amendments must be approved by the IRB prior to implementation.

9.3 Informed Consent

All participants must be provided a consent form describing the study with sufficient information for each participant to make an informed decision regarding their participation. Participants must sign the IRB-approved informed consent form prior to participation in any study specific procedure. The participant must receive a copy of the signed and dated consent document.

The original signed copy of the consent document must be retained in the medical record or research file.

9.4 Changes in the Protocol

Once the protocol has been approved by the UCSF IRB, any changes to the protocol must be documented in the form of an amendment. The amendment must be signed by the PI and approved by PRC and the IRB prior to implementation.

If it becomes necessary to alter the protocol to eliminate an immediate hazard to participants, an amendment may be implemented prior to IRB approval. In this circumstance, however, the PI must then notify the IRB according to institutional requirements. The Study Chair and the UCSF study team will be responsible for updating any participating sites.

9.5 Handling and Documentation of Clinical Supplies

The UCSF Principal Investigator and each participating site will maintain complete records showing the receipt, dispensation, return, or other disposition of all investigational drugs at the site. The date, quantity and batch or code number of the drug, and the identification of participants to whom the investigational product has been dispensed by participant number and initials will be included.

The Principal Investigator at each participating site shall not make the investigational drug available to any individuals other than to qualified study participants. Furthermore, the PI at each study site will not allow the investigational drug to be used in any manner other than that specified in this protocol.

9.6 Case Report Forms (CRFs)

The Principal Investigator and/or his/her designee, at each study site, will prepare and maintain adequate and accurate participant case histories with observations and data pertinent to the study. Study specific Case Report Forms (CRFs) will document safety and treatment outcomes for safety monitoring and data analysis. All study data will be entered into OnCore® via standardized CRFs in accordance with the CTMS study calendar, using single data entry with a secure access account. Study personnel for each study site will complete the CRFs; the PI for the study site will review and approve the completed CRFs.

The information collected on CRFs shall be identical to that appearing in original source documents. Source documents will be found in the patient's medical records maintained by study personnel at each study site. All source documentation should be kept in separate research folders for each patient.

In accordance with federal regulations, the PI at each study site is responsible for the accuracy and authenticity of all clinical and laboratory data entered onto CRFs. The PI will approve all completed CRFs to attest that the information contained on the CRFs is true and accurate.

The PI at each study site will be responsible for ensuring the accurate capture of study data. At study completion, when the CRFs have been declared to be complete and accurate, the database will be locked. Any changes to the data entered into the CRFs after that time can only be made by joint written agreement among the Study Chair, and the trial statistician.

All source documentation and CTMS data will be available for review/monitoring by the UCSF DSMC and regulatory agencies.

9.7 Oversight and Monitoring Plan

The UCSF Helen Diller Family Comprehensive Cancer Center DSMC will be the monitoring entity for this study. The UCSF DSMC will monitor the study in accordance with the NCI-approved Data and Safety Monitoring Plan (DSMP). The DSMC will routinely review all adverse events and suspected adverse reactions considered "serious". The DSMC will audit study-related activities to ensure that the study is conducted in accordance with the protocol, local standard operating procedures, FDA regulations, and Good Clinical Practice (GCP). Significant results of the DSMC audit will be communicated to the IRB and the appropriate regulatory authorities at the time of continuing review, or in an expedited fashion, as applicable. See Appendix 2 Data and Safety Monitoring Plan for a Phase 2 or 3 Institutional Study, for additional information.

The PI at each study site will be responsible for ensuring the accurate capture of study data. At study completion, when the CRFs have been declared to be complete and accurate, the database will be locked. Any changes to the data entered into the CRFs after that time can only be made by joint written agreement among Study Chair and the trial statistician.

9.8 Multicenter communication

The UCSF Coordinating Center provides administration, data management, and organizational support for the participating sites in the conduct of a multicenter clinical trial. The UCSF Coordinating Center for Phase II studies will also coordinate, at minimum, monthly conference calls with the participating sites at the completion of each cohort or more frequently as needed to discuss risk assessment. The following issues will be discussed as appropriate:

- Enrollment information
- Cohort updates (i.e. DLTs)
- Adverse events (i.e. new adverse events and updates on unresolved adverse events and new safety information)
- Protocol violations
- Other issues affecting the conduct of the study

9.9 Record Keeping and Record Retention

The PI at each study site is required to maintain adequate records of the disposition of the drug, including dates, quantity, and use by subjects, as well as written records of the disposition of the drug when the study ends.

The PI at each study site is required to prepare and maintain adequate and accurate case histories that record all observations and other data pertinent to the investigation on each individual administered the investigational drug or employed as a control in the investigation. Case histories include the case report forms and supporting data including, for example, signed and dated consent forms and medical records including, for example, progress notes of the physician, the individual's hospital chart(s), and the nurses' notes. The case history for each individual shall document that informed consent was obtained prior to participation in the study.

Study documentation includes all CRFs, data correction forms or queries, source documents, Sponsor-Investigator correspondence, monitoring logs/letters, and regulatory documents (e.g., protocol and amendments, IRB correspondence and approval, signed participant consent forms).

Source documents include all recordings of observations or notations of clinical activities and all reports and records necessary for the evaluation and reconstruction of the clinical research study.

In accordance with FDA regulations, the PI at each study site shall retain records for a period of 2 years following the date a marketing application is approved for the drug for the indication for which it is being investigated; or, if no application is to be filed or if the application is not approved for such indication, until 2 years after the investigation is discontinued and FDA is notified.

9.10 Coordinating Center Documentation of Distribution

It is the responsibility of the Study Chair to maintain adequate files documenting the distribution of study documents as well as their receipt (when possible). The HDFCCC recommends that the Study Chair maintain a correspondence file and log for each segment of distribution (e.g., FDA, drug manufacturer, participating sites, etc.).

Correspondence file: should contain copies (paper or electronic) of all protocol versions, cover letters, amendment outlines (summary of changes), etc., along with distribution documentation and (when available) documentation of receipt.

Correspondence log: should be a brief list of all documents distributed including the date sent, recipient(s), and (if available) a tracking number and date received.

At a minimum, the Study Chair must keep documentation of when and to whom the protocol, its updates and safety information are distributed.

9.11 Regulatory Documentation

Prior to implementing this protocol at UCSF or any participating site, the protocol, informed consent form, HIPAA authorization and any other information pertaining to participants must be approved by the UCSF IRB. Prior to implementing this protocol at the participating sites, approval for the UCSF IRB approved protocol must be obtained from the participating site's IRB.

The following documents must be provided to UCSF HDFCCC before the participating site can be initiated and begin enrolling participants:

- Participating Site IRB approval(s) for the protocol, appendices, informed consent form and HIPAA authorization
- Participating Site IRB approved consent form
- Participating Site IRB membership list
- Participating Site IRB's Federal Wide Assurance number and OHRP Registration number
- Curriculum vitae and medical license for each investigator and consenting professional
- Documentation of Human Subject Research Certification training for investigators and key staff members at the Participating Site
- Participating site laboratory certifications and normals
- Upon receipt of the required documents, UCSF HDFCCC will formally contact the site and grant permission to proceed with enrollment.

10 Protection of Human Subjects

10.1 Protection from Unnecessary Harm

Each clinical site is responsible for protecting all subjects involved in human experimentation. This is accomplished through the IRB mechanism and the process of informed consent. The IRB reviews all proposed studies involving human experimentation and ensures that the subject's rights and welfare are protected and that the potential benefits and/or the importance of the knowledge to be gained outweigh the risks to the individual. The IRB also reviews the informed consent document associated with each study in order to ensure that the consent document accurately and clearly communicates the nature of the research to be done and its associated risks and benefits.

Appendix 1 Performance Status Criteria

ECOG Performance Status Scale		Karnofsky Performance Scale	
Grade	Descriptions	Percent	Description
0	Normal activity Fully active, able to carry on all pre-disease performance without restriction	100	Normal, no complaints, no evidence of disease
		90	Able to carry on normal activity; minor signs or symptoms of disease
1	Symptoms, but ambulatory Restricted in physically strenuous activity, but ambulatory and able to carry out work of a light or sedentary nature (e.g., light housework, office work)	80	Normal activity with effort; some signs or symptoms of disease
		70	Cares for self, unable to carry on normal activity or to do active work
2	In bed < 50% of the time Ambulatory and capable of all self-care, but unable to carry out any work activities Up and about more than 50% of waking hours	60	Requires occasional assistance, but is able to care for most of his/her needs
		50	Requires considerable assistance and frequent medical care
3	In bed > 50% of the time Capable of only limited self-care, confined to bed or chair more than 50% of waking hours	40	Disabled, requires special care and assistance
		30	Severely disabled, hospitalization indicated Death not imminent
4	100% bedridden Completely disabled Cannot carry on any self-care Totally confined to bed or chair	20	Very sick, hospitalization indicated Death not imminent
		10	Moribund, fatal processes progressing rapidly
5	Dead	0	Dead

Appendix 2 Data and Safety Monitoring Plan: Multicenter Phase 2 or 3 Trial with Safety Lead-In

1. Oversight and Monitoring Plan

The UCSF Helen Diller Family Comprehensive Cancer Center (HDFCCC) Data and Safety Monitoring Committee (DSMC) is responsible for auditing data quality and participant safety for all HDFCCC institutional clinical studies. A summary of DSMC activities for this study includes:

- Review of all participant data in safety lead-in phase.
- Approval to enroll past safety lead-in phase by DSMC Chair or Vice Chair.
- Semiannual auditing after safety lead-in phase (depending on accrual).
- Review of serious adverse events.
- Minimum of a biennial regulatory auditing visit.

2. Monitoring and Reporting Guidelines

The Principal Investigator at the UCSF Coordinating Center will hold the role of Study Chair. The Study Chair is responsible for the overall conduct of the trial and for auditing its safety and progress at all participating sites. The Study Chair will conduct continuous review of data and participant safety at monthly UCSF Site Committee meetings. The discussions are documented in the UCSF Site Committee meeting minutes.

All institutional Phase II or III therapeutic studies with a lead-in are designated with a high-risk assessment during the safety lead-in phase and a moderate risk assessment. During the safety lead-in phase, the DSMC will audit all visits through the first cycle of treatment for all participants enrolled in this phase of the trial.

After the completion of enrollment in the safety lead-in phase, the Study Chair will submit a report to the DSMC Chair outlining all AEs, SAEs, and DLTs (as defined in the protocol) with a request to proceed onto the next phase of the trial. Within two business days of receipt, the DSMC Chair or designee will review the report and issue written authorization to proceed or a request for more information. The report is then reviewed at the subsequent DSMC meeting.

After DSMC authorization to enroll beyond the safety lead-in phase is granted, study data is audited by a DSMC Monitor/Auditor on a semiannual basis with a random selection of twenty percent of the participants (or at least three participants if the calculated value is less than three). The DSMC Monitor/Auditor will audit a maximum of 5 cycles of treatment in the participants selected for review or until the selected participants discontinue study participation or the trial is closed with the IRB. Additionally, the assigned DSMC Monitor/Auditor will review no more than 10 total participant charts during the course of auditing this trial. DSMC Monitor/Auditors will send a follow-up report to the study team within 20 business days after the auditing visit is complete for the PI and the study team to resolve all action items from this report within 20 business days. An abbreviated regulatory review (i.e., reviewing protocol and consent versions, SAEs, PVs, DOA logs, 1572 forms, etc.) will occur at each participant monitoring review; however, a full regulatory review will occur on a biennial basis by the DSMC for regulatory compliance.

The participating site's source documents are audited remotely via either review of redacted source documents downloaded by the site into the CRA console of OnCore and/or via access to the site's electronic medical records. The DSMC Monitor/Auditor will audit no more than three participant charts at each participating site during the course of auditing this trial.

Auditing of all enrolled participants in these trials will be complete after 20% of enrolled participants have been audited through five cycles of treatment. However, regulatory reviews of the trial, safety reviews (i.e., Serious Adverse Event (SAE) reviews and Protocol Violation (PV) reviews), and audit/inspection preparation (as applicable) will continue until the trial is closed by the IRB.

Multicenter communication

The UCSF Coordinating Center includes the UCSF PI (Study Chair) and the UCSF study team. The UCSF Coordinating Center provides administration, data management, and organizational support for the participating sites in the conduct of a multicenter clinical trial. The UCSF Coordinating Center will also coordinate monthly conference calls with the participating sites. The following issues will be discussed as appropriate:

- Enrollment information.
- Adverse events (i.e., new adverse events and updates on unresolved adverse events and new safety information).
- Protocol Violations.
- Other issues affecting the conduct of the study.

Adverse events reporting to the DSMC will include reports from both the UCSF Coordinating Center, as well as the participating sites. The data (i.e., copies of source documents) from the participating sites will be downloaded into the PC console of OnCore prior to the remote monitoring visits in order for the DSMC to monitor the participating site's compliance with the protocol and applicable FDA regulations.

3. Review and Oversight Requirements

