 - **Dose Level 1** (Atezolizumab 1200 mg x 3 cycles, Tiragolumab 600 mg x 3 cycles): There will be an initial safety lead in of 6 patients treated with this regimen, at which time enrollment will pause to assess the safety of this combination treatment. As long as no more than 1 out of the initial 6 patients experience dose limiting toxicities (DLTs) or a delay in the time to radical cystectomy, the remaining patients will enroll at the same dose and regimen.
 - If two or more patients out of the initial six experience DLTs within the first cycle (3 weeks), accrual will be halted and the combination reevaluated.
 - If two or more patients out of the initial six experience DLTs within the first 2 cycles (6 weeks), accrual to this dose level will be halted and we will move to dose level 3.
 - If two or more patients out of the initial six experience DLTs or delay in the time to radical cystectomy, and no more than 1 patient experienced DLTs during the first 2 cycles (6 weeks), the next six patients will be treated at dose level 2
 - **Dose Level 2** (Atezolizumab 1200 mg x 3 cycles, Tiragolumab 600 mg x 2 cycles): As long as no more than 1 out of 6 patients experience DLTs or a delay in the time to radical cystectomy with this treatment, the remaining patients will enroll at the same dose and regimen.
 - If two or more patients out of the six patients experience DLTs within the first cycle (3 weeks), accrual will be halted and the combination reevaluated.
 - If two or more patients out of the six experience DLTs or delay in the time to radical cystectomy, and no more than 1 patient experienced DLTs during the first cycle (3 weeks), the next six patients will be treated at dose level 3
 - **Dose Level 3** (Atezolizumab 1200 mg x 3 cycles, Tiragolumab 600 mg x 1 cycle): This will be the selected regimen if no more than 1 out of 6 patients experience DLTs or a delay in the time to radical cystectomy. However if 2 or more patients experience DLTs or a delay in the time to radical cystectomy with this combination regimen, then accrual will be halted and the combination reevaluated.
- Expansion: Once the intended treatment regimen is established following completion of the safety assessment, an additional 15 patients will be enrolled at the same regimen for a total of 21 patients on that treatment regimen.

Cohort B Safety Lead-in Schema

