5.1.1 Other Modalities or Procedures

A radical cystectomy per institutional standard of care is planned for all patients enrolling in this study. No other procedures following initiation of systemic treatment (e.g., TURBT) are required for subjects while on study. Cystectomy may be performed beginning 3 weeks after the last planned dose of study therapy is administered. See study calendar (Section 6.10) for schedule of evaluations.

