5.4 Dose Limiting Toxicities (DLTs)

Dose Limiting Toxicity (DLT) is an unacceptable treatment-related toxicity that occurs between time of first dose and time of cystectomy, defined as:

- any Grade 4 toxicity, or
- any recurrent Grade 3 toxicity, or
- any Grade 3 toxicity persisting more than 2 weeks, or
- any toxicity that results in delay of cystectomy beyond 12 weeks from the first dose of study drug

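### Sections 3.1, 5.4, 5.5 and Appendix 2 disagree on how much follow-up the six Cohort B lead-in patients need before the expansion is released

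*Combined protocol and SAP*

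**What the plan says.** **The decision rule.** Section 3.1 treats six patients at a dose level, "at which time enrollment will pause to assess the safety of this combination treatment", and lets the remaining patients enrol at that regimen only if at most one of the six has a DLT or a delay to cystectomy. At the first dose level, separate branches count DLTs within 3 weeks and within 6 weeks. Section 5.4 defines a DLT as an "unacceptable treatment-related toxicity that occurs between time of first dose and time of cystectomy", and one of its components is "any toxicity that results in delay of cystectomy beyond 12 weeks from the first dose of study drug".

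**The timing of the review.** Section 5.5 places the safety review, for the Cohort B lead-in as well as Cohort A, after all six patients of a dosing cohort have been accrued and given at least one dose. It adds ongoing review if serious treatment-related toxicity or delay is seen. The reason it gives is the known safety profile of atezolizumab.

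**The timing of the authorisation.** Appendix 2, section 2: "After the completion of enrollment in the safety lead-in phase, the Study Chair will submit a report to the DSMC Chair", a report "outlining all AEs, SAEs, and DLTs (as defined in the protocol) with a request to proceed onto the next phase of the trial". Then: "Within two business days of receipt, the DSMC Chair or designee will review the report and issue written authorization to proceed", or ask for more information. On source checking in the lead-in, "the DSMC will audit all visits through the first cycle of treatment for all participants enrolled in this phase of the trial".

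**A contrast.** Section 5.2 records that in Cohort A the next dose level opened only after the six patients below had finished treatment and had their cystectomy. Cohort B has no equivalent sentence.

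**The concern.** The go rule can be fully applied only when all six patients have reached cystectomy or passed week 12. At the points named in Section 5.5 and Appendix 2, the sixth patient may have had a single dose. Whether that patient's surgery will be delayed past 12 weeks is unknown, the 6-week branch cannot be evaluated for that patient, and the earlier patients are at various points in their windows.

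No section says how long the pause lasts, or that the Study Chair's request must wait for the sixth patient's window to close. A team following 5.5 and Appendix 2 to the letter could count DLTs on partial data, find one or none, and obtain authorisation for 15 more patients treated with curative intent. Events that have not yet happened count as absent, so the rule loses part of its ability to hold back a regimen that is too toxic.

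**Working it through.** **1. The plan's own threshold.** 2/6 = 33.3% and 1/6 = 16.7%. Releasing at one or fewer of six therefore matches the stop at 33.3% or more in Sections 5.5 and 8.2. The two rules agree; the disagreement is over when the count is taken.

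**2. Length of the DLT window.** Three doses every 3 weeks fall at weeks 0, 3 and 6. "Cystectomy may be performed beginning 3 weeks after the last planned dose of study therapy is administered", so the earliest surgery is at week 9, and the delay criterion runs to week 12. Cycle 1 is 3 weeks, that is 3/12 = 25% to 3/9 = 33% of the window.

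**3. Release with the complete window.** For true DLT risk p, P(at most 1 of 6) = (1−p)^6 + 6p(1−p)^5.
- p = 1/3: 64/729 + 192/729 = 0.351
- p = 0.5: 1/64 + 6/64 = 0.109

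**4. Follow-up at the review.** Section 3.6 expects 11–16 months to accrue Cohort B, and Section 3.2 gives 21–33 patients. With 4.348 weeks per month:
- 16 × 4.348 / 33 = 2.11 weeks between patients
- 11 × 4.348 / 21 = 2.28 weeks between patients

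If the review falls L weeks after the sixth patient starts and g is the gap, the follow-up of the six is min(12, L + g·i) for i = 0 to 5. With g = 2.11 and L = 0 this is 0, 2.1, 4.2, 6.3, 8.4 and 10.5 weeks, or 44% of the total DLT patient-time (47% with g = 2.28). No patient has reached 12 weeks. With L = 3 the share is 67–69%, and one or two of the six have reached 12 weeks.

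**5. Release with incomplete follow-up.** Assumption: DLT onset is even over 12 weeks, so a patient followed for t weeks has shown a DLT with probability q = p·t/12. P(release) = Π(1−q_i) + Σ q_i Π_{j≠i}(1−q_j).

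Example with p = 1/3, g = 2.11, L = 0: q = 0, 0.059, 0.117, 0.176, 0.234, 0.293. P(no DLT) = 0.371 and P(one DLT) = 0.419, so release = 0.790.

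| True DLT risk | Full window | Sixth patient starts (L = 0) | Sixth patient ends cycle 1 (L = 3) |
|---|---|---|---|
| 20% | 0.66 | 0.90–0.91 | 0.81–0.82 |
| 33.3% | 0.35 | 0.76–0.79 | 0.58–0.60 |
| 50% | 0.11 | 0.56–0.60 | 0.32–0.34 |

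**6. Sensitivity at p = 1/3.**
- Slower accrual, 21 patients in 16 months (g = 3.31): 0.65 at L = 0, 0.52 at L = 3.
- Pauses taken out of the accrual period (one of 12 weeks, g = 1.71; or 36 weeks in all, g = 1.02): 0.85–0.94 at L = 0, 0.65–0.77 at L = 3.
- All DLT risk falling within 9 weeks instead of 12 (replace 12 by 9 in steps 4 and 5, g = 2.11–2.28): 0.67–0.69 at L = 0, 0.50 at L = 3.

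Every case is above 0.35, but the size moves a good deal with accrual and onset.

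**The case against.** The best defence is that Section 3.1 is the trial-specific rule and already solves the problem. Enrolment pauses, and the criterion refers to events that cannot be known before cystectomy, so a careful team would wait. Appendix 2 says the report follows completion of enrolment, which sets an earliest point and no deadline. The two business days bind the DSMC's reply, not the Study Chair's submission. All of this is correct, and it makes the defect a contradiction between sections rather than a plan that looks only at early data. It does not remove the defect, because Section 5.5, in the body of the protocol, names a review point after as little as one dose.

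A reader might also infer three stronger things, which the documents do not support.
- *That the DSMC decides on cycle 1 alone.* The cycle 1 audit is a check of charts. Authorisation rests on a report of all protocol-defined DLTs. Appendix 2 also lists review of all lead-in participant data and allows a request for more information. Still, a report cannot list events that have not yet occurred, and asking for more is optional.
- *That most DLTs would be unseen at release.* At the planned pace slightly more than half of the DLT patient-time is unseen when the sixth patient starts, but only about a third after that patient's cycle 1. Applying one early fraction to all six patients would ignore their staggered entry.
- *That all 15 expansion patients would be exposed unprotected.* In the 12 weeks after the sixth patient starts, about 12/2.28 = 5.3 to 12/2.11 = 5.7 further patients would begin. The 33.3% rule stays active, and the DSMC reviews serious events on an ongoing basis. These limits act only after further patients have been treated.

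**Conclusion.** The conflict is real and worth correcting. Sections 3.1 and 5.4 define release on events up to cystectomy and delay beyond 12 weeks; Section 5.5 and Appendix 2 permit the review and the request to proceed before those events can be known for the later patients. If the earlier timing is followed, the chance of releasing a regimen at the plan's own 33.3% limit rises from 0.35 to about 0.76–0.79 at close of lead-in enrolment, or to about 0.58–0.60 after the sixth patient's first cycle. At a true risk of 50% it rises from 0.11 to 0.56–0.60 or 0.32–0.34.

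The direction does not depend on the assumptions; the size does. The figures rest on the Section 3.6 pace holding during the lead-in and on even DLT onset over 12 weeks. The documents give no DLT rate and no onset pattern, so the true rates of 20–50% are a stated range. If the team in practice waits until the Section 3.1 rule can be fully applied, the full-window column holds and only the text needs correcting.

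**What to change.** Reconcile Sections 3.1, 5.4 and 5.5 and Appendix 2, section 2, so that the safety review, the Study Chair's report and the DSMC authorisation all use the same DLT observation window as the decision rule they apply. State how long the enrolment pause lasts, and align the lead-in audit, now limited to cycle 1, with that window. Amending Appendix 2 alone would leave the contradiction in Section 5.5. The choice of window is for the sponsor and the DSMC; the need is that one window applies throughout.

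The cost is a wording change, somewhat longer chart review for the lead-in patients, and a pause at each dose level tested that the Section 3.1 rule already implies. If each pause ran 12 weeks from the sixth patient's first dose, three levels would take up to 36 weeks. That should be checked against Section 3.6. Fitting 33 patients into 16 months with 36 weeks of pauses needs one patient every (16 × 4.348 − 36)/33 = 1.02 weeks. Fitting 21 into 11 months with one 12-week pause needs one every (11 × 4.348 − 12)/21 = 1.71 weeks. If those rates are not realistic, the accrual estimate should be revised as well.
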